8.2.2 UC-Related Corticosteroids

The UC-related corticosteroids intercurrent event is defined as follows.

- subjects not on UC-related corticosteroids (systemic or locally acting corticosteroids for UC) at Baseline who initiated UC-related corticosteroids during the Induction Study;

- subjects on UC-related systemic corticosteroids at Baseline who have dosages increased to greater than the prednisone equivalent dose of corticosteroid taken at Baseline, or initiation of any rectal corticosteroids during the Induction Study regardless of rectal corticosteroid dose;
- subjects on UC-related rectal corticosteroids at Baseline who have dosages increased to greater than the dose taken at Baseline, or initiation of any new type of rectal or any systemic corticosteroids during the Induction Study.

The time point of the UC-related corticosteroids intercurrent event is defined as the date when one of the scenarios above occurs for a subject. As such, subjects will be considered as "non-responder" for binary endpoints at or after the occurrence of the UC-related corticosteroids intercurrent event through the end of the Induction Study. For continuous endpoints, all measurements at or after the occurrence of the UC-related corticosteroids intercurrent event through the end of the Induction Study will not be used in the analysis.

8.3 Handling of Missing Data

Missing data could occur due to various reasons, including missing visits/assessments, early withdrawal from the Induction Study, or missing due to COVID-19 infection or logistical restrictions.

The COVID-19 pandemic is interfering with the conduct of many ongoing trials, with potential impacts on treatment duration and the collection, analysis and the interpretation of clinical trial data. Some protocol-specified visits in the clinical trials may be impacted due to COVID-19 infection or logistical restrictions during the pandemic. For example, some scheduled visits may be missed due to self-quarantine or local government restrictions on travel; some visits may also be delayed or canceled due to healthcare resource constraints during the pandemic. Impacted visits due to COVID-19 will be recorded in the database. The probability of having missed visits and missing data due to COVID-19 infection or logistical restrictions related to the COVID-19 pandemic can be reasonably assumed to be unrelated to the unobserved values. Therefore, for the purpose

of statistical analysis, it is reasonable to assume that these missing data are missing at random (MAR) and the statistical models that require MAR assumption are appropriate. The intent is to provide reliable estimates of the treatment effects under the scenario without the impact of COVID-19 pandemic.

Handling of missing data for the efficacy analyses is described below.

8.3.1 Categorical Endpoints

[figure not shown]
[figure not shown]
For binary efficacy endpoints, missing data will be handled using the following approaches:

- The primary approach for handling missing data in the analysis of binary endpoints will use **Non-Responder Imputation** while incorporating Multiple Imputation (MI) to handle missing data due to **CCOVID-19 (NRI-C)**.

The NRI-C will categorize any subject who does not have an evaluation during a pre-specified visit window (either due to missing assessment or due to early withdrawal from the study) as a non-responder for the visit. The only exception is that missing data due to COVID-19 infection or logistical restrictions related to the COVID-19 pandemic will be handled by Multiple Imputation (MI). At each visit, subjects will be characterized as responders or non-responders based on MI imputed values if missing due to COVID-19; otherwise, subjects will be considered as non-responders for missing due to other reasons in the NRI-C approach. In addition, at or after the occurrence of the UC-related corticosteroids intercurrent event (see Section 8.2), subjects will be counted as non-responders.

- A sensitivity analysis for categorical endpoints will use **NR**I**** with **No** special data handling for missing due to **CCOVID-19 (NRI-NC)**.

NRI-NC will be performed in the same way as NRI-C without the exception above. Missing due to COVID-19 infection or logistical restrictions will also be counted as non-responders. Subjects at or after the occurrence of the UC-related corticosteroids intercurrent event will still be counted as non-responders. This is the same method as the "NRI" defined in the protocol.

-
- Hybrid Multiple Imputation Method (HMI): Sensitivity analysis will be performed using hybrid multiple imputation method for the primary endpoint. Subjects who discontinue study drug prior to Week 8 due to lack of efficacy or AEs and have no available measurements will be considered as "non-responder" for clinical remission. Subjects who discontinue for other reasons and have no available measurements will be categorized according to the data from multiple imputations.
 - Multiple Imputation (MI) for NRI-C and HMI: Markov Chain Monte Carlo (MCMC) will be first applied to augment data into monotonic missing pattern, where applicable, and PROC MI will be used to generate 30 datasets using the regression method. The variables to be included in the imputation model are: treatment group, stratification factors (bio-IR status (bio-IR vs. non-bio-IR), Baseline corticosteroid use (yes vs. no) and Baseline Adapted Mayo score (≤ 7 vs. > 7)), Baseline measurement, and if applicable, post-baseline measurements at each visit up to the end of the analysis period. The random seed for MCMC and the random seed for PROC MI are specified in [Appendix D](#). The imputed post-baseline measurements will be rounded to the same precision as the observed data before the determination of responder status. Subjects will be characterized as responders or non-responders based on MI imputed datasets. Using the CMH model adjusted by stratification factors (bio-IR status (bio-IR vs. non-bio-IR), Baseline corticosteroid use (yes vs. no) and Baseline Adapted Mayo score (≤ 7 vs. > 7)), the imputed endpoints will be analyzed using each of the 30 datasets. SAS PROC MIANALYZE will be used to generate the final inferences of the risk difference between upadacitinib treatment group and placebo group, using Rubin's rule. 

 - As Observed (AO): The AO analysis will not impute values for missing evaluations, and thus a subject who does not have an evaluation on a scheduled
-

visit will be excluded from the AO analysis for that visit. AO will include all values collected in the study.

8.3.2 Continuous Endpoints

For continuous endpoints, missing data will be handled using Mixed-Effect Model Repeat Measurement (MMRM).

The MMRM will be conducted using mixed model including observed measurements at all visits, except that measurements at or after the occurrence of UC-related corticosteroids intercurrent event will be excluded (see Section 8.2.2). The mixed model includes the categorical fixed effects of treatment, visit and treatment-by-visit interaction, randomization stratification factors (bio-IR status [bio-IR vs. non-bio-IR], Baseline corticosteroid use [yes vs. no] and Baseline Adapted Mayo score [≤ 7 vs. > 7]), and the continuous fixed covariates of Baseline measurements. An unstructured variance covariance matrix (UN) will be used. If the model cannot converge, an autoregressive (1) covariance structure matrix will be used. The parameter estimations are based on the method of restrictive maximum likelihood (REML). The fixed effects will be used to report model-based means at corresponding visits.

8.4 Primary Efficacy Endpoint and Analyses

8.4.1 Primary Efficacy Endpoint

The primary efficacy endpoint is the achievement of clinical remission per Adapted Mayo score at Week 8. The primary estimand is the difference in the percentage of subjects achieving clinical remission per Adapted Mayo score at Week 8 regardless of premature discontinuation of study drug and without initiation or dose escalation of UC-related corticosteroids (See Section 8.2.2) in the upadacitinib 45 mg QD and placebo groups in the ITT population. Details of the estimand definitions are outlined in [Appendix E](#).

8.4.2 Handling of Missing Data for the Primary Efficacy Endpoint

The NRI-C will be the primary approach for missing data handling in the analyses of the primary efficacy endpoint.

The NRI-NC and HMI approaches will be used as sensitivity analyses.

8.4.3 Primary Efficacy Analysis

The primary analysis will compare the proportion of subjects achieving clinical remission in upadacitinib treatment group and placebo group in the ITT1 population. The difference between the treatment groups in the primary efficacy endpoint will be assessed using the CMH test and will be stratified by bio-IR status (bio-IR vs. non-bio-IR), Baseline corticosteroid use (yes vs. no) and Baseline Adapted Mayo score (≤ 7 vs. > 7). A CMH based two-sided 95% confidence interval for the difference between treatment groups will be calculated.

8.4.4 Additional Analyses of the Primary Efficacy Endpoint

For the primary efficacy endpoint, the same CMH analysis as detailed in Section 8.1 will be performed using As Observed (AO) data handling without any imputation as an additional analysis. The analysis will be conducted on the ITT1 population who have the efficacy measurement at Week 8 visit.

For the primary efficacy endpoint, a supplementary analysis will be conducted to evaluate the potential impact of deviations. In this analysis, subjects with deviations that could potentially impact the analysis of primary endpoint will be excluded. The criteria will be fully defined in the classification plan. Exclusion of subjects will be adjudicated by the therapeutic area medical director (TAMD) and reasons for the subjects to be excluded will be documented and finalized before the Induction Study database lock for the primary analysis. Treatment difference between upadacitinib 45 mg QD and placebo with point estimate and 95% CI will be presented using NRI-C approach with the CMH method as detailed in Section 8.1.

8.5 Secondary Efficacy Analyses

8.5.1 Key Secondary Efficacy Analyses

The key secondary endpoints are defined in Section 3.2. The estimands corresponding to the secondary efficacy endpoints are defined in Section 2.1. Details of the estimand definitions are outlined in Appendix E. For ITT1 Population, secondary efficacy endpoints in Part 1 will be analyzed by comparing upadacitinib treatment group and placebo group. The binary secondary endpoints will be analyzed by CMH and the corresponding analyses are specified in Section 8.3.1. The NRI-C will be the primary approach for missing data handling in the analyses of binary secondary efficacy endpoints. The NRI-NC approach will be used as sensitivity analyses.

The continuous secondary endpoints will be analyzed by MMRM and the corresponding analyses are specified in Section 8.3.2.

8.5.2 Supportive Secondary Efficacy Analyses

The secondary efficacy endpoints will also be analyzed for ITT1 population using As Observed (AO) data handling without any imputation. The categorical endpoints and continuous endpoints will be analyzed by CMH and MMRM, respectively, and the corresponding analyses are specified in Section 8.1.

8.6 Additional Efficacy Analyses

Additional efficacy endpoints are defined in Section 3.3. The estimands corresponding to the additional efficacy endpoints are defined for each of the binary additional endpoints as follows: difference in the percentage of subjects achieving binary endpoints; regardless of premature discontinuation of study drug and without initiation or dose escalation of UC-related corticosteroids (See Section 8.2.2) in the upadacitinib 45 mg QD and placebo groups in the ITT population. The estimands corresponding to the additional efficacy endpoints are defined for each of the continuous additional endpoints as follows: difference in the mean change from baseline regardless of premature discontinuation of study drug and if subjects would not initiate or escalate dose of UC-related corticosteroids

(See Section 8.2.2) in the upadacitinib 45 mg QD and placebo groups in the ITT population. For ITT1 Population, additional efficacy endpoints in Part 1 will be analyzed by comparing upadacitinib treatment group and placebo group. The categorical endpoints and continuous endpoints will be analyzed by CMH and MMRM (or ANCOVA), respectively, and the corresponding analyses are specified in Section 8.2. The NRI-C approach will be used for missing data handling in the analyses of categorical efficacy endpoints.

For ITT2 population, descriptive statistics will be provided for additional efficacy endpoints in Part 2. The NRI-C approach will be used for missing data handling in the analyses of categorical efficacy endpoints.

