5.3.3.3 Additional Variables

In Substudies 1 and 2, additional efficacy variables are as follows and will be evaluated.

- Proportion of subjects achieving response in IBDQ Bowel Symptom domain (increase of IBDQ bowel symptom domain score ≥ 6) at Week 8
- Proportion of subjects with UC-related hospitalizations through Week 8
- Proportion of subjects with UC-related surgeries through Week 8
- Proportion of subjects achieving response in IBDQ fatigue item (increase of IBDQ fatigue item score ≥ 1) at Week 8
- Proportion of subjects with SFS of 0, RBS of 0 and endoscopic subscore of 0 at Week 8
- Proportion of subjects with SFS of 0, RBS of 0 and endoscopic subscore of ≤ 1 at Week 8
- Proportion of subjects achieving clinical remission per Full Mayo Score (defined as a full Mayo score ≤ 2 with no sub-score > 1) at Week 8
- Change in Full Mayo Score from Baseline to Week 8
- Proportion of subjects achieving clinical remission per Partial Mayo score over time.
- Proportion of subjects achieving clinical response per Partial Adapted Mayo score over time
- Proportion of subjects achieving clinical response per Partial Mayo score over time.
- Proportion of subjects with SFS ≤ 1 over time.
- Proportion of subjects with RBS = 0 over time.
- Proportion of subjects with SFS ≤ 1 at Week 2.
- Proportion of subjects with RBS of 0 at Week 2.
- Proportion of subjects with fecal calprotectin below 150 mg/kg over time.
- Change from Baseline in fecal calprotectin over time
- Change from Baseline in hs-CRP over time.
- Change from Baseline in Partial Adapted Mayo score, Partial Mayo score and SFS, RBS over time.
- Change from Baseline in UCEIS score over time.

- Change from Baseline in laboratory and nutritional parameters (e.g., hemoglobin, hematocrit, albumin, total protein concentration, and weight).
- Change from Baseline in subject-reported stool frequency (absolute values).
- Change from Baseline in IBDQ total and domain score over time.
- Change from Baseline in individual IBDQ item under Bowel Symptom domain (for Q1, Q5, Q9, Q13, Q17, Q20, Q22, Q24, Q26, and Q29) over time.
- Proportion of subjects with IBDQ response (increase of IBDQ ≥ 16 from Baseline) over time.
- Proportion of subjects with IBDQ remission (IBDQ total score ≥ 170) over time.
- Change from Baseline in EQ-5D-5L score over time.
- Change from Baseline in WPAI scores over time.

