8.6 Additional Efficacy Analyses

Additional efficacy endpoints are defined in Section 3.3.

The estimands corresponding to the additional efficacy endpoints are defined for each of the binary additional endpoints as follows: difference in percentage of subjects achieving binary endpoints regardless of premature discontinuation of study drug and without use of

UC-related rescue medications (See Section 8.2.2) in the upadacitinib 15 mg QD, upadacitinib 30 mg QD and placebo groups in the ITT_A population.

The estimands corresponding to the additional efficacy endpoints are defined for each of the continuous additional endpoints as follows: difference in mean change from baseline regardless of premature discontinuation of study drug and if subjects would not use UC-related rescue medications (See Section 8.2.2) in the upadacitinib 15 mg QD, upadacitinib 30 mg QD and placebo groups in the ITT_A population.

The estimands corresponding to UC-related hospitalization and surgery incidence rates is as follows: difference in the incidence rate through Week 52 regardless of premature discontinuation of study drug or use of UC-related rescue medications in the upadacitinib 15 mg QD, upadacitinib 30 mg QD and placebo groups in the ITT_A population.

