3.3 Other Efficacy Endpoints

The following additional efficacy endpoints will be evaluated for Part 1:

- The achievement of response in IBDQ Bowel Symptom domain (defined as increase of IBDQ bowel symptom domain score ≥ 6 from Baseline) at Week 8;
- The achievement of response in IBDQ fatigue item (defined as increase of IBDQ fatigue item score ≥ 1 from Baseline) at Week 8;
- The achievement of SFS of 0, RBS of 0 and endoscopic subscore of 0 at Week 8;
- The achievement of SFS of 0, RBS of 0 and endoscopic subscore of ≤ 1 at Week 8;
- The achievement of clinical remission per Full Mayo score at Week 8;
- Change in Full Mayo score from Baseline at Week 8;
- The achievement of clinical remission per Partial Mayo score over time;
- The achievement of clinical response per Partial Adapted Mayo score over time;
- The achievement of clinical response per Partial Mayo score over time;
- The achievement of SFS ≤ 1 over time;
- The achievement of RBS of 0 over time;

- The achievement of Fecal calprotectin below 150 mg/kg over time;
- Change from Baseline in fecal calprotectin over time;
- Change from Baseline in hs-CRP over time;
- Change from Baseline in Partial Adapted Mayo score, Partial Mayo score and SFS, RBS over time;
- Change from Baseline in UCEIS score over time;
- Change from Baseline in laboratory and nutritional parameters (e.g., hemoglobin, hematocrit, albumin, total protein concentration, and weight);
- Change from Baseline in subject-reported stool frequency (absolute values) over time;
- Change from Baseline in IBDQ total and domain score over time;
- Change from Baseline in individual IBDQ item under Bowel Symptom domain (for Q1, Q5, Q9, Q13, Q17, Q20, Q22, Q24, Q26, and Q29) over time;
- The achievement of IBDQ response (defined as increase of IBDQ total score ≥ 16 from Baseline) over time;
- The achievement of IBDQ remission (defined as IBDQ total score ≥ 170) over time;
- Change from Baseline in EQ-5D-5L score over time;
- Change from Baseline in WPAI scores over time;
- Change from Baseline in SF-36 Physical Component Summary (PCS) and Mental Component Summary (MCS) components and domain scores over time;
- Summary of PGIC improvement category over time;
- Summary of PGIS severity category over time;
- Change from Baseline in FACIT-F score over time;
- Change from Baseline in UC-SQ score over time;
- UC-related hospitalizations through Week 8;
- UC-related surgeries through Week 8;
- All-cause hospitalizations through Week 8;

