- All-cause surgeries through Week 8.

The following additional efficacy endpoints will be evaluated for Part 2:

- The achievement of clinical remission per Adapted Mayo score at Week 16;
- The achievement of endoscopic improvement at Week 16;
- The achievement of endoscopic remission at Week 16;
- The achievement of clinical response per Adapted Mayo score at Week 16;
- The achievement of clinical response per Partial Adapted Mayo score at Week 10;
- The achievement of histologic-endoscopic mucosal improvement at Week 16;
- The achievement of no bowel urgency at Week 16;
- The achievement of no abdominal pain at Week 16;
- The achievement of histologic improvement at Week 16;
- Change from Baseline in IBDQ total score at Week 16;
- The achievement of mucosal healing at Week 16;
- Change from Baseline in FACIT-F score at Week 16.

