- Proportion of subjects with fecal calprotectin below 150 mg/kg over time.
- Proportion of subjects with IBDQ response (increase of IBDQ ≥ 16 from Baseline) over time.
- Change from Baseline in hs-CRP over time.
- Change from Baseline in fecal calprotectin over time
- Change from Baseline in Adapted Mayo score, Full Mayo score, Partial Mayo score and Mayo subscores over time.
- Change from Baseline in UCEIS score over time.
- Proportion of subjects with histologic remission (defined as Geboes score < 2) at Weeks 8 and 44.
- Change from Baseline in histologic score over time.
- Change from Baseline in laboratory and nutritional parameters (e.g., hemoglobin, hematocrit, albumin, total protein concentration, and weight).
- Change from Baseline in subject-reported stool frequency (absolute values).
- Change from Baseline in IBDQ score over time.
- Change from Baseline in EQ-5D-5L score over time.
- Change from Baseline in WPAI scores over time.
- Change from Baseline in SF-36 PCS, MCS components and domain scores over time.
- Change in PGIC score over time.

- Change from Baseline in FACIT-F score over time.
- Change from Baseline in UC-SQ score over time
- Health care resource utilization (UC-related hospitalizations and surgeries) during the study.

For categorical efficacy endpoints, the pairwise comparisons for the difference in proportions of subjects between treatment groups and placebo group will be analyzed using the CMH test adjusted for previous biologic use, baseline corticosteroid use and baseline Adapted Mayo score (≤ 7 and > 7). Additionally, the CMH based two-sided 95% confidence interval (CI) for the difference in the proportions between the treatment groups and placebo group will be provided.

The non-responder imputation will be used for subjects with missing data at the endpoint evaluated. The last observation carried forward (LOCF) method will also be used as the sensitivity analyses for the secondary endpoints.

Continuous secondary efficacy variables will be analyzed using an Analysis of Covariance (ANCOVA) model including factors for treatment group and stratification variables. Baseline values will be used as a covariate in the ANCOVA models.

Both last observation carried forward (LOCF) and observed case (OC) analyses will be used for continuous endpoints when conducting ANCOVA analysis. The LOCF analysis is considered primary for inferential purposes. HCRU will be analyzed as observed only.

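### Substudy 2 SAP 8.6 puts hospitalisation and surgery under the steroid rule and NRI-C without an exception, and never says what non-response means for a harmful event

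*SAP*

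**What the plan says.** The items are in Substudy 2 SAP 3.3, in the Part 1 list of additional endpoints. The list includes "UC-related hospitalizations through Week 8" and ends with "All-cause surgeries through Week 8"; UC-related surgeries and all-cause hospitalisations make up the four. Protocol 5.3.3.3 shows the type of variable: "Proportion of subjects with UC-related hospitalizations through Week 8". Each is therefore binary, and the numerator holds subjects who had the event.

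Substudy 2 SAP 8.6 sets a single estimand for all binary additional endpoints: the between-arm difference in the percentage achieving the endpoint, with corticosteroid initiation or escalation for UC counting against achievement. On method it says "The categorical endpoints and continuous endpoints will be analyzed by CMH and MMRM (or ANCOVA), respectively", and on missing data "The NRI-C approach will be used for missing data handling in the analyses of categorical efficacy endpoints".

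The consequences are in 8.2.2 and 8.3.1. Under NRI-C, a subject without an evaluation in the visit window is a non-responder unless the gap is due to COVID-19. In addition, "at or after the occurrence of the UC-related corticosteroids intercurrent event (see Section 8.2), subjects will be counted as non-responders". Section 12.0 tests additional endpoints at a nominal two-sided 0.05.

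The other two SAPs treat these events differently. Substudy 3 SAP 8.6 defines a separate estimand, "difference in the incidence rate through Week 52 regardless of premature discontinuation of study drug or use of UC-related rescue medications". Substudy 1 SAP 10.3 says "HCRU will be analyzed as observed only".

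**The concern.** Non-responder rules are written for favourable outcomes. They are conservative because a subject with missing data, or one who needed steroids, is denied a success. For a harmful event that logic breaks down: denying the outcome gives the subject a good result, and imposing it invents an admission or an operation.

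The steroid rule matters most because it overrides recorded data and does not merely fill gaps. A subject who starts steroids during a flare and is then admitted has a documented hospitalisation, yet 8.2.2 and 8.3.1 replace it with a non-responder code. At stake is a between-arm comparison with a nominal p-value, computed on a variable that does not measure how often subjects were hospitalised or operated on.

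**Working it through.** The plan states no figure on this point, so the check is mainly a trace through the text. The arithmetic only shows how each coding behaves.

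**1. Does an exception exist in Substudy 2?** None appears in 3.3, 8.2.2, 8.3.1 or 8.6. The As Observed analyses in 8.4.4 and 8.5.2 cover the primary and ranked secondary endpoints only. Section 8.2.1 keeps data after study drug discontinuation, so stopping drug alone does not trigger the problem. Steroid events, and missing evaluations or study withdrawal for non-COVID reasons, do.

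**2. Which way is a non-responder coded?** The Substudy 2 SAP does not say. The estimand's achieving language places a non-responder outside the numerator, which means no event. Protocol 8.1.3 calls subjects with a steroid event a *failure* for categorical endpoints, which for a harm can mean having the event.

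**3. What does each coding estimate?** For each arm, let *h* be the recorded event rate, *s* the share of those events that the rule recodes, and *i* the proportion of subjects with a steroid event or a non-COVID missing evaluation (*i* ≥ *hs*). Subscripts *p* and *u* mark placebo and upadacitinib.

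- No-event coding: rate = *h*(1 − *s*). The difference becomes (*h_u* − *h_p*) + (*h_p s_p* − *h_u s_u*).
- Failure coding: rate = *h*(1 − *s*) + *i*.

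Neither equals *h* unless *s* = 0 or, for failure coding, *i* = *hs*.

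**4. Illustration.** All rates are assumed, because the documents give none: *h* = 5% placebo and 1% upadacitinib (true difference −4.0 points), with *s* equal in both arms.

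| *s* | No-event coding (%) | Diff. | Failure, *i* = 6% / 3% | Diff. | Failure, *i* = 12% / 4% | Diff. |
|---|---|---|---|---|---|---|
| 25% | 3.75 v 0.75 | −3.0 | 9.75 v 3.75 | −6.0 | 15.75 v 4.75 | −11.0 |
| 50% | 2.50 v 0.50 | −2.0 | 8.50 v 3.50 | −5.0 | 14.50 v 4.50 | −10.0 |
| 75% | 1.25 v 0.25 | −1.0 | 7.25 v 3.25 | −4.0 | 13.25 v 4.25 | −9.0 |
| 100% | 0 v 0 | 0 | 6.00 v 3.00 | −3.0 | 12.00 v 4.00 | −8.0 |

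The −4.0 in the third row is a coincidence of the inputs; both arm rates there are still wrong. With unequal shares even the sign can change: *s_p* = 100% and *s_u* = 25% give 0 v 0.75%, a difference of +0.75.

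**5. What is not affected?** These endpoints lie outside the fixed sequence in Substudy 2 SAP 12.0. The sample size rests on clinical remission (5% v 18%, 154 and 308 subjects). Exact enumeration of Fisher's test gives 98.9% power there, consistent with the stated figure above 95%.

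**The case against.** The strongest reply is that this machinery was never meant for these items.

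- Other binary endpoints in 3.3 are worded as achievements, whereas these four are plain event listings.
- The data come from the health-care-use form attached to adverse event reporting (Protocol Appendices C and G), not from a score at a visit.
- The NRI-C seed table in Appendix D goes as far as PGIC and PGIS but names no hospitalisation or surgery variable.

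This suggests that multiple imputation was not planned for them. It does not exempt them from non-responder scoring or the steroid rule, and 8.6 states both without limit.

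The second reply concerns consequence, and most of it stands. Hospital admission is a serious adverse event by definition (Protocol 6.1.1.2), and Substudy 2 SAP 9.1, 9.2.2 and 9.2.5 report serious events by arm without imputation. Surgery without admission may be missed there.

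Third, a reader might infer that early withdrawals hide recorded events. Under no-event coding they do not: a hospitalisation recorded before withdrawal is an observation, not a missing value. A subject who leaves with nothing recorded is event-free under a plain observed count too, unless the denominator is adjusted.

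Fourth, a reader might infer that both other SAPs already contain one common exemption. Only Substudy 3 expressly sets aside rescue and discontinuation, and it uses events over time at risk. Substudy 1's as-observed wording turns off imputation but does not expressly lift the steroid censoring in its Section 6.0, and it compares percentages with a chi-square test.

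**Conclusion.** The point holds as a defect in a stated rule, not as missing detail: 8.6 applies to these four endpoints as written, and each available coding gives something other than the event rate. The steroid override is the firmest part under either reading. Withdrawal and non-COVID missingness distort the result only under failure coding.

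Two stronger readings are tempting and unsupported. One is that the plan definitely scores these subjects as event-free; the SAP leaves the direction undefined, and the protocol's wording points the other way. The other is that affected subjects are mostly on placebo, so that the treatment difference shrinks by a known amount. The documents give no event, steroid-start or withdrawal rates by arm, so neither the size nor the direction of the bias can be fixed; the table above rests on assumed inputs throughout.

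The reach is limited. The endpoints are unranked and tested at nominal alpha, and no primary or ranked result, alpha allocation or power figure changes. The correction is still worth making because the planned comparison is wrong as written and easily repaired.

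**What to change.** Add to Substudy 2 SAP 8.6:

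- UC-related and all-cause hospitalisations and surgeries are counted as observed through Week 8, regardless of corticosteroid use or study drug discontinuation.
- Section 8.2.2 and NRI-C do not apply to these four endpoints, and the generic binary estimand is replaced by one that says so.
- The handling of subjects who leave the study before Week 8 is stated. One option is first events over time at risk, as in Substudy 3 SAP 8.6, with follow-up ending at Week 8 or study withdrawal. If a simple proportion is kept, its denominator should be named.

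The cost is two or three SAP sentences and a small programming change. The events are already collected on the health-care-use form, so no new data, visits or sample size are needed.
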